Research plan, translated from Swedish, including a statistical analysis plan

A controlled study of weighted chain blankets

Document Date: November 1, 2015

Scientific description

Purpose

The primary aim is to investigate whether the nightly use of a weighted chain blanket has a significantly better effect on sleep time, total sleep time and daytime fatigue for patients with sleep disturbance in psychiatric disease compared to a light chain blanket (equivalent to placebo) after four weeks of use. Secondary issues are whether treatment with weighted chain blanket results in a significantly better effect than a light blanket for objectively measured sleep and subjectively assessed anxiety, depression, and pain.

Hypotheses

The use of the weighted chain blanket allows:

1. Sleep time decreases.
2. Sleep stays longer with fewer wake-ups during the night.
3. The sleep becomes calmer
4. The sleep becomes less tense
5. Pain decreases daytime
6. Pain decreases at night
7. Anxiety and anxiety decrease daytime
8. Anxiety and anxiety decrease at night
9. Fatigue decreases daytime
10. Concentration capacity increases daytime

Primary outcome measures

The patient's subjective symptoms of sleep and day fatigue will be evaluated by the Insomnia Sleep Inventory (ISI) and the Fatigue Scale Inventory (FSI) scales. It will also be evaluated by the patient's self-assessed values in the self-assessment rating scale developed by Stockholm Utility for evaluating ball and chain blankets (hereafter referred to as "rating scale for weighted blankets"). Depression and anxiety will be evaluated with the scale Hospital Anxiety and Depression Scale (HAD). Objective sleep parameters will be recorded with actigraphs.

Chief researcher

Responsible for the study of patients with bipolar disorder and/or ADHD is [name], leg. Occupational Therapist at the Affective Section, Psychiatry Southwest of Stockholm County Council (SLSO) and [name], Medical Doctor and Chief Physician and Section Manager at the Affective Section, Psychiatry Southwest in Stockholm County Council (SLSO)

Overview

Sleep difficulties are one of the most common reasons for people seeking medical attention. People with sleeping problems often report a great deal of suffering and a negative impact on activity. It has also been found that it increases the risk of other diseases. It also affects the ability to work, which causes high social costs (1-5). Several major studies have shown that between 15 and 50% of the

adult population report that they have sleep disturbances and that it is an increasing problem (1.5.6). Mainly there are sleep difficulties, difficulty in maintaining sleep, as well as nightmares that have been reported. Concerning patients in psychiatry, there is a strong link between sleep disorders and depression/anxiety (7-13). For patients with bipolar disorder, about 70% report that they have sleep disorders (14-15). The traditionally accepted methods of pharmacologically treating these patients and CBT do not always yield success (10, 14). Untreated or ineffective treatment often leads to chronic sleep disorders (1, 9, 10).

Occupational therapists work with activity and activity disorders (16). The condition for being active is that you have a good sleep. Therefore it is natural that occupational therapists also work with sleep disorders.

Prescription of ball and chain blankets is a common occupational therapy intervention (17-21). According to the SBU (22), the purpose of the blankets is to create a sense of security and calmness, but that the scientific evidence is insufficient to assess the effect of weight loss in sleep disorders caused by motor and/or mental anxiety. However, in cost-benefit assessments, cognitive aids and weighted covers for people with mental disabilities have found a clear positive financial outcome for both the user, state, municipality, county council and the general economy (23), due to a decrease in the need for help and the number of sick leave days. People can stay or introduce themselves to work and self-reliance increases.

In summary, the test/prescription of the ball and chain blankets is a promising, relatively new, method for adults with sleep disorders.

Project plan

Patients

Patients with sleep disorders and motor / mental anxiety will be recruited at the Affective section at Psychiatry South West. Patients who are expected to use the chain blankets after assessment by the attending physician will be included after informed consent. All patients who accepted inclusion and who received a chain blanket will be included in the analysis.

Inclusion and exclusion criteria

We intend to recruit patients from Psychiatry Southwest with affective and anxiety diagnoses and/or ADHD, which are simultaneously bothered by sleep disturbance and anxiety/anxiety. Patients are recruited from open and inpatient wards. They should have one of the diagnoses Bipolar Disorder Type I, Type II Bipolar Disorder, Recurrent Depression, Panic Syndrome, Social Phobia, General Anxiety Disorder (GAD) and/or ADHD. They should also have a clinically significant sleep disorder, i.e., a rating of 14 or more on ISI. Exclusion criteria are ongoing drug abuse, consumption of sleep medication beyond recommended levels (> 7.5 mg zopiclone or 10 mg zolpidem) or cognitive problems that make the patient unable to complete the study.

Characteristics of patient material

The examined group will be characterized by age, sex, choice of cover, weight, diagnosis, comorbid diagnosis and duration of disease.

Procedure

After the patient has received oral information and signed a written informed consent, characterization of the patient material will be made. The study will be conducted in four phases. The first week they use their usual blanket (baseline). Sleep, fatigue, anxiety, and depression will be recorded with the scales mentioned above. Then a second part follows four weeks when they use the blanket randomized to (Week 2-5). In the second phase, patients are randomized to either get a 6 or 8 kg lining blanket or a lightweight cover of approximately 1.5 kg of the same appearance in which light plastic chains are sewn in. This cover is of such low weight that it corresponds to a regular blanket and therefore acts as a placebo control. Randomization and instruction, as well as collection of blankets after four weeks of use, will be carried out by a person who does not perform the ratings at inclusion and follow-up. Patients should maintain their medication unchanged during the study period. They are followed up by telephone every week. At the telephone interview information about how they used the blanket will be gathered, and patients will estimate their sleep with the scales mentioned above. After four weeks of use of the blanket, the final visit for the randomized study will be conducted, and data (scales and actigraph) from this visit is the primary outcome of the study.

In the third phase, all patients are offered an open-follow up study in a 4-week (week 6-9) where they can choose freely between ball and chain weighted blankets. After these four weeks, everyone is called for a second visit with new estimates and collection of actigraph data of (week 9). In the fourth phase, patients who wish to continue with one of the weighted blankets will be offered to do so. After 12 months, patients who choose to continue using weighted blankets will be contacted by telephone to check the extent to which they use the blanket and are asked to estimate the same symptoms as before.

Power Calculation

In a previously uncontrolled pilot study of weighted-duty non-control groups, the average sleep time decreased from 98 minutes (SD 69) to 31 minutes (SD 28). Based on these results, calculating the effect of the blanket for a future study where the placebo deck had no effect, and the active blanket would have the same effect as in the pilot study figures would want a power of 0.9 with a significance level of 0.05, only 15 subjects would be required in the study. However, we have no data on the effect of sleep on sleep measured with the ISI scale. Nor is it likely that the placebo blanket would not have any effect at all. However, we expect that patient material of about 100 individuals should be enough to find a significant effect.

Statistical analysis

Comparison between the effect on the groups will be performed after four weeks and eight weeks with conventional methods of statistical significance testing in controlled and randomized studies. All patients who used the blanket for at least one night will be included in the analysis (equivalent to "intention to treat"). Data from patients who discontinue treatment will be asked if they can accept to participate in follow-up in the same way as if they had completed treatment. In these cases, data are included in the analysis as measured. Secondly, Last Observation Carried Forward (LOCF) or other established statistical method is used to handle data from patients who interrupt treatment.

Self-assessed values before, after eight weeks and 12 months will be analyzed with and at eight weeks after with paired t-test for dependent variables. When data distribution does not match normal distribution, the analysis will be supplemented by non-parametric tests.

Timetable

The study will extend over three years.

Safety monitoring

Clinical monitoring will be done by treatment staff on the Affective section in consultation with the patient.

Ethical considerations

Testing/ordination of the chain blanket in sleep disorders, as well as motor anxiety and/or mental anxiety, is a well-known occupational therapy intervention. The method appears effective and has no significant adverse effects. However, the method is not sufficiently illuminated and scientifically tested. The use of the clinical data recorded as part of routine follow-up will be unidentified and therefore does not present a disadvantage to the patient. All procedures will be done with informed consent, data will be processed with confidentiality and unidentified. We believe that the disadvantages of the patients are small.

Possible impact

Sleep disturbances caused by anxiety are one of the common causes of suffering for patients with psychiatric diagnoses. If it is confirmed in this study that the chain blankets can reduce this disorder for the patient group without having any side effects of treatment, it will represent a very big step forward for the treatment of sleep disturbances.

References

2. Cappuccio F,ea. Sleep Duration and All-Cause Mortality: A Systematic Review and Meta-Analyses of Prospective Studie.pdf>. Sleep. 2010;33(5).

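### HAD and actigraphy are secondary in Purpose but primary in the outcome section and Procedure, and no measure is named to decide the primary aim

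*Protocol*

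**What the plan says.** - **Purpose** sets the primary aim as "a significantly better effect on sleep time, total sleep time and daytime fatigue for patients with sleep disturbance in psychiatric disease", compared with the light blanket after four weeks. It then lists as secondary whether the weighted blanket has "a significantly better effect than a light blanket for objectively measured sleep and subjectively assessed anxiety, depression, and pain".
- **Primary outcome measures** begins in line with that aim: "subjective symptoms of sleep and day fatigue will be evaluated by the Insomnia Sleep Inventory (ISI) and the Fatigue Scale Inventory (FSI) scales", together with a rating scale for weighted blankets. Under the same heading it continues: "Depression and anxiety will be evaluated with the scale Hospital Anxiety and Depression Scale (HAD). Objective sleep parameters will be recorded with actigraphs". The document has no heading for secondary outcomes.
- **Procedure** says of the four-week visit that "data (scales and actigraph) from this visit is the primary outcome of the study". Earlier in that section, anxiety and depression are among the items recorded with the scales, so HAD is covered by that word.
- **Power Calculation** works from pilot sleep time in minutes and then concedes that "we have no data on the effect of sleep on sleep measured with the ISI scale".
- **Statistical analysis** says the comparison of the groups "will be performed after four weeks and eight weeks with conventional methods of statistical significance testing in controlled and randomized studies". It names no lead measure, order of testing, co-primary rule or adjustment. The title line says that the document contains its statistical analysis plan.

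**The concern.** There are two linked defects.

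The first is a contradiction. HAD and actigraphy are secondary in one section and primary in two others. Suppose self-reported sleep and fatigue show no difference at four weeks but HAD or actigraphy does. The outcome section and Procedure would allow this to be reported as a positive primary result; Purpose would make it a secondary finding beside a negative primary one. The headline conclusion would turn on which sentence is cited.

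The second remains after the first is repaired. The primary aim has three unranked constructs and three unranked instruments (ISI, FSI, rating scale), and no instrument is assigned to sleep time or total sleep time. The power paragraph does not settle the matter: it has figures for sleep time only and treats ISI as a different measure without effect data. If success on any one instrument may be claimed, the false-positive risk exceeds that of a single test.

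**Working it through.** **Status of each measure, side by side**

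| Measure | Purpose | Primary outcome measures | Procedure, four-week visit |
|---|---|---|---|
| ISI, FSI, rating scale | primary aim, by construct | listed | primary (scales) |
| HAD | secondary (anxiety, depression) | listed | primary (through the word scales) |
| Actigraphy | secondary (objective sleep) | listed | primary (named) |

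The first row is consistent. The other two are not.

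**The plan's own figure.** The only calculated sample size is 15, from pilot sleep time of 98 minutes (SD 69) falling to 31 minutes (SD 28), at power 0.9 and significance level 0.05. The difference is 98 − 31 = 67. The pooled SD is √[(69² + 28²)/2] = √2772.5 = 52.65. The normal formula gives 2 × [52.65 × (1.960 + 1.282)/67]² = 12.98, so 13 per arm; the exact two-sided t-test gives 15 per arm. The figure is thus reproduced per arm, on sleep time. It says nothing about ISI, FSI, HAD or actigraphy, so it does not identify the lead measure.

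**False-positive risk.** Assumptions, neither stated nor excluded by the protocol:
- one test per instrument, each two-sided at 0.05;
- any one significant result counts as success;
- test statistics are standard normal with a common correlation r.

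For k instruments with no true effect, the chance of at least one significant result in favour of the weighted blanket is

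1 − ∫ φ(u) · Φ[(1.960 − √r·u)/√(1 − r)]^k du,

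which for r = 0 is 1 − 0.975^k. For example, 1 − 0.975³ = 0.073 and 1 − 0.975⁵ = 0.119.

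| Tests | r = 0 | r = 0.5 | r = 0.7 | r = 0.9 |
|---|---|---|---|---|
| One | 2.5% | 2.5% | 2.5% | 2.5% |
| Three (ISI, FSI, rating scale) | 7.3% | 6.3% | 5.5% | 4.2% |
| Five (plus HAD, actigraphy) | 11.9% | 9.1% | 7.4% | 5.1% |

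Counting both directions, against 5% for one test, three instruments give 14.3%, 12.5%, 10.9% and 8.4%; five give 22.6%, 18.3%, 14.8% and 10.2%. The scales overlap and come from the same patients, so the correlated columns are the more realistic.

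**After the fix.** One lead measure restores 2.5% in the favourable direction. Two primaries under Holm give 2.5%, 2.3%, 2.1% and 1.8% at the four correlations (first step at 0.0125 in the favourable tail).

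**Sensitivity.** Assume 50 per arm (about 100 patients, 1:1, no dropout). The standardised difference detectable with 90% power is (z for the two-sided level + 1.282) × √(2/50). At level 0.05 this is 3.242 × 0.2 = 0.65. Bonferroni over three instruments (0.0167 each) raises it to 0.735, and over five (0.01 each) to 0.77. Power at a difference of 0.65 falls from 0.90 to 0.80 and 0.75.

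**The case against.** The strongest reply is that Purpose is the only section that uses both ranks, and it ranks clearly. The outcome section follows the same order, so in a translated document its heading may be a careless title over a list of instruments. The Procedure sentence mainly serves to separate the four-week randomised visit from the later open phase, and it reaches HAD only through a general word. This narrows the conflict but does not remove it: the heading says primary, the actigraph is named in the primary-outcome sentence, and no text subordinates either measure.

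Test order and multiplicity adjustment are commonly left to a statistical analysis plan. On its own, their absence would carry little weight, although this document says it includes that plan. Which outcome is primary is a protocol matter, and a later plan would inherit the two conflicting statements.

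The inflation figures depend on a rule found nowhere in the text. Purpose joins its three constructs with the word and, which can be read as requiring all of them; there would then be no inflation. That stands. The figures illustrate what the open wording permits and do not carry the finding. The count of one test per instrument is also an assumption. It may be too low, since HAD covers both anxiety and depression and actigraphy is described as giving several parameters.

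**Conclusion.** The concern holds and must be fixed. The conflicting status of HAD and actigraphy is plain from the text and needs no assumption. The missing lead measure is equally plain: the four-week visit, the instruments and most hypothesised directions are fixed, but the deciding outcome is not.

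The size is conditional. If any one result may count, the favourable false-positive risk lies between 5.1% and 11.9% for five instruments and between 4.2% and 7.3% for three, over correlations from 0.9 down to 0. Removing HAD and actigraphy from the primary set therefore reduces the problem without solving it.

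**What to change.** 1. Under Primary outcome measures, keep only measures of the primary aim. Move HAD and actigraphy to a new heading for secondary outcome measures, as Purpose implies.
2. In Procedure, state that only the primary measure or measures at the four-week visit are the primary outcome, and that the other scales and the actigraph data are secondary.
3. Before any outcome is compared by arm, name one lead outcome; the choice is the sponsor's. The ISI total score is a candidate: ISI is listed first and supplies the entry criterion of 14 or more. Sleep time is another, being the only outcome with pilot figures, but both the variable and its instrument must then be defined. The protocol counts a decrease in it as benefit and lists it beside total sleep time, so it probably means time to fall asleep. Alternatively, keep a short primary set such as ISI and FSI, with a fixed order or Holm.
4. Use the same wording in Purpose, outcome measures and Procedure, and say which instrument yields sleep time and total sleep time. The three constructs can stay in the primary aim.

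The cost is text only: no new data, visits or patients. The downside is that a positive result on HAD, actigraphy or another non-lead scale can no longer be called primary. If ISI leads, the sample of about 100 was not calculated for it. With two primaries under Holm, the first step is tested at 0.025 rather than 0.05. A fixed order keeps the first test at 0.05 but allows the second only if the first succeeds.

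### Both inpatients and outpatients are recruited, but care setting is neither listed for recording nor used in randomisation or analysis: a modest loss of precision at week 4, and an added contribution to change in the uncontrolled paired tests

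*Protocol*

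**What the plan says.** The protocol's section on inclusion and exclusion criteria states that "Patients are recruited from open and inpatient wards". It gives no expected share or cap for either setting. The section on characteristics of patient material then lists what will describe the sample: "The examined group will be characterized by age, sex, choice of cover, weight, diagnosis, comorbid diagnosis and duration of disease". Care setting is not on that list.

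Under Procedure, the baseline week is spent under the patient's usual blanket, with no statement of what this means for someone on a ward. After that, "patients are randomized to either get a 6 or 8 kg lining blanket or a lightweight cover of approximately 1.5 kg"; no stratification factor and no allocation ratio are given. On follow-up, "They are followed up by telephone every week", to collect blanket use and sleep ratings. The same section says "Patients should maintain their medication unchanged during the study period". Admission and discharge are not mentioned. The visit after four weeks on the allotted blanket supplies the primary outcome.

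Under Statistical analysis, the groups are to be compared "with conventional methods of statistical significance testing in controlled and randomized studies", with no covariate named. There is also a within-patient analysis: "Self-assessed values before, after eight weeks and 12 months will be analyzed with and at eight weeks after with paired t-test for dependent variables". It has no control group.

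**The concern.** A patient recruited on a ward may improve more over the following weeks than an outpatient, whichever blanket is used, because the episode resolves or because the patient goes home. If so, setting predicts the outcome, and the plan neither balances it, nor removes its variance, nor lists it for recording.

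The consequences differ between the two analyses. In the randomised comparison, setting adds noise and may by chance be uneven between arms, in a trial of about 100. In the paired before-after tests there is no second arm to cancel the recovery, so it becomes part of the change observed under the blanket. The baseline week adds an ambiguity: if some patients spend it on a ward and are at home later, their place of sleep and their blanket change together.

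What is recorded and how patients are allocated must be settled before enrolment. An analysis plan cannot supply them afterwards.

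**Working it through.** **The plan's own figures.** The plan gives no figure on care setting. Its one computed figure, 15 subjects, plays no part here. It reproduces as a per-group number: difference 98 - 31 = 67 minutes, pooled SD sqrt((69² + 28²)/2) = 52.65, and a two-sided two-sample t-test at 0.05 with power 0.9 gives 14.01, rounded up to 15. The figure used below is the planned total of about 100.

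**Assumptions, none of them in the documents.** Allocation 1:1, so 50 per arm; two-sided test at 0.05; inpatient share p from 10% to 50%; inpatients improve by D = 0.5 to 1.0 within-setting SD more than outpatients, equally in both arms; a true blanket effect of 0.65 SD, chosen because it gives 90% power when setting is accounted for.

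**Formulas.**
- Chance imbalance: the number of inpatients falling in one arm of 50 is hypergeometric (100 patients, 100p inpatients).
- Variance inflation if setting is ignored: v = 1 + p(1 - p)D².
- Power: Φ(0.65 / (sqrt(2/50) × sqrt(v)) - 1.96). With v = 1 this is Φ(3.25 - 1.96) = 90.1%.
- Added mean change in the paired tests: p × D.

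| p | Imbalance ≥10 points | Imbalance ≥20 points | v, D = 0.5 | Power | v, D = 1.0 | Power | p × D (SD) |
|---|---|---|---|---|---|---|---|
| 10% | 9.2% | 0.1% | 1.02 | 89.5% | 1.09 | 87.6% | 0.05-0.10 |
| 20% | 21.1% | 2.3% | 1.04 | 89.0% | 1.16 | 85.5% | 0.10-0.20 |
| 30% | 27.5% | 4.9% | 1.05 | 88.6% | 1.21 | 84.0% | 0.15-0.30 |
| 50% | 31.7% | 7.1% | 1.06 | 88.4% | 1.25 | 82.8% | 0.25-0.50 |

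As a check on the last row: 3.25/sqrt(1.25) - 1.96 = 0.947, and Φ(0.947) = 82.8%.

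**Size of a given imbalance.** A 10-point difference in inpatient share shifts the estimated arm difference by 0.10 × D = 0.05 to 0.10 SD. The standard error with 50 per arm is sqrt(2/50) = 0.20 SD.

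**Type I error.** In 20,000 simulated trials of 100 patients with no blanket effect, D = 1.0 and setting ignored, the unadjusted t-test rejected in 5.0% (30% inpatients) and 5.1% (50% inpatients).

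**Imbalance and noise are one loss.** Take 30% inpatients, 4 extra ISI points and a residual SD of 6 (also assumed; D = 4/6 = 0.67). The SD of the chance bias is 4 × sqrt(4 × 0.3 × 0.7/100) = 0.367. Variance inflation is 1 + 0.21 × 16/36 = 1.093. The variance of the arm difference without setting is 2 × 36/50 = 1.44, and the increase is 1.44 × 0.0933 = 0.134 = 0.367². The two figures are the same quantity, and an unadjusted test already carries it in its standard error. In the paired tests the same inputs add 0.3 × 4 = 1.2 ISI points.

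**The case against.** The strongest reply is that the primary result is a randomised comparison against a light blanket. Recovery and discharge occur in both arms and cancel in expectation. Unstratified randomisation is valid at this size, mixing settings is a legitimate pragmatic choice, and covariates are often left to an analysis plan. All of this stands for the validity of the week-4 test. It does not answer the loss of precision, nor the need to fix recording and allocation beforehand. The protocol's title also says that it contains the statistical analysis plan.

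Several stronger statements are tempting, and the documents do not support them:
- A reader might infer that discharge and recovery bias the primary result in favour of the blanket. They do not; that reading fits only the uncontrolled paired tests.
- A reader might take the list of characteristics as closed, so that adjustment is impossible. The text does not exclude other items, and the recruiting unit is presumably known at recruitment.
- A reader might assume that inpatients are acutely ill, spend the baseline week in a ward bed and go home during the trial, or that setting is strongly prognostic. These are plausible inferences only. The protocol says where patients are recruited, not where they sleep, and unchanged medication and telephone follow-up may point to more stable patients.

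It is also fair to say that the weakness of the paired tests is not specific to setting. Entry requires an ISI rating of 14 or more, so regression to the mean and natural course enter the change as well. Recording setting does not cure that.

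**Conclusion.** The point holds as a cheap improvement, not as a flaw that invalidates the primary analysis. Setting is missing from the listed characteristics, the randomisation and the analysis, although both settings are recruited. At week 4 the cost is about 1 to 7 points of power, together with a 9-32% chance of an imbalance of at least 10 points that could not readily be examined afterwards. These describe one loss and should not be added together. The upper end needs half the sample to be inpatients and a full 1 SD setting effect. In the paired tests to eight weeks and 12 months, the addition to the mean change is 0.05-0.5 SD under the same assumptions, and it does not shrink with sample size.

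All these sizes rest on an assumed inpatient share and setting effect, and on reading the translated word for open care as outpatient. If few inpatients enrol, or they improve no faster than outpatients, the effect is close to nil.

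**What to change.** - Record care setting at randomisation, and add a question on admission or discharge to the existing weekly call.
- Stratify the randomisation by setting and include setting as a covariate in the week-4 comparison.
- State what the usual-blanket baseline week means for a patient on a ward.
- Report the paired before-after results as descriptive, shown by setting.

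The cost is one field, one extra question, two randomisation lists and one model term. Delaying the start for inpatients or leaving them out is not needed for this purpose: it would change the recruited population or the timeline, and the paired tests would still have no control.

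### The light cover is called a placebo but is matched to the heavy blanket in appearance only, so a week-4 difference on self-rated scales cannot be separated from expectation

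*Protocol*

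**What the plan says.** The Purpose section sets the primary aim as a comparison of the weighted chain blanket with the light one: "compared to a light chain blanket (equivalent to placebo) after four weeks of use". Under Procedure, "patients are randomized to either get a 6 or 8 kg lining blanket or a lightweight cover of approximately 1.5 kg of the same appearance". The light cover holds plastic chains, and the reason it counts as a placebo is given in one sentence: "This cover is of such low weight that it corresponds to a regular blanket and therefore acts as a placebo control".

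Three other statements bear on the point.

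- **Baseline.** Immediately before randomisation, patients spend a week under their own bedding: "The first week they use their usual blanket (baseline".
- **Staff.** Randomisation, instruction and collection of blankets "will be carried out by a person who does not perform the ratings at inclusion and follow-up".
- **Weekly calls.** "At the telephone interview information about how they used the blanket will be gathered, and patients will estimate their sleep with the scales mentioned above". The caller is not named.

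Under Primary outcome measures the protocol lists ISI, FSI, the rating scale for weighted blankets and HAD, with actigraphs for objective sleep. Procedure takes the primary data, scales and actigraph together, from the visit after four weeks of use. Power Calculation accepts that the control blanket probably has some effect. The protocol plans no expectation rating and gives no instruction to patients about disclosing their blanket.

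**The concern.** A placebo control has two jobs: it leaves out the active ingredient, and it keeps patients from knowing that it has been left out. The protocol's reasoning covers the first job. For the second it offers only a matching appearance, while the ingredient left out is one that patients feel. The property used to justify the label, that the cover is like a regular blanket, is also the property most likely to give the allocation away.

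This matters because the main scales record what patients say about their own sleep, fatigue, mood and anxiety. If patients know or suspect their arm, hope in one arm and disappointment in the other can move those ratings without any effect of weight. A significant result would then be reported as weight beating placebo, although the design did not isolate weight.

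A smaller, related concern is the weekly call. The protocol separates the person who randomises from the person who rates. It then has blanket use and sleep ratings collected in one telephone interview without saying who holds it.

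**Working it through.** **Step 1: how alike are the two covers?** Weights are from Procedure.

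- Ratio: 6/1.5 = 4.0 and 8/1.5 = 5.3.
- Difference: 6 − 1.5 = 4.5 kg and 8 − 1.5 = 6.5 kg.

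The stated match is appearance. Nothing in the protocol matches or disguises weight. The patient's most recent reference is a week under the usual blanket, and the protocol itself says that the light cover corresponds to a regular one. A patient in the light arm is therefore likely to notice no change in weight, and a patient in the heavy arm is likely to notice a large one.

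**Step 2: whose knowledge do the safeguards limit?** Keeping the randomiser away from the ratings limits what the rater knows. It does nothing about what the patient knows, and with self-rated scales that matters most.

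**Step 3: how much could expectation alone do?** The protocol gives no figure for this, so the calculation is an illustration on stated assumptions.

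Inputs:
- N of about 100 and significance level 0.05 (Power Calculation).
- 50 per arm (assumption; no allocation ratio is given).
- Two-sided test (assumption; sidedness is not given).
- True effect of weight: zero (by construction).
- Between-arm shift in self-ratings from expectation, b = 0.2, 0.3 or 0.4 SD (assumption).

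Formula: for a two-sample t-test with 98 degrees of freedom, the noncentrality is b/√(2/50) = b/0.2, and the two-sided critical value is 1.984. The probability of p<0.05 is the noncentral-t mass beyond ±1.984.

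| b (SD) | Noncentrality | P(p<0.05) |
|---|---|---|
| 0 | 0 | 5% |
| 0.2 | 1.0 | 16.8% |
| 0.3 | 1.5 | 31.8% |
| 0.4 | 2.0 | 50.8% |

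Almost all of this probability lies on the side favouring the heavy blanket.

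**Step 4: compare with the effect the trial can detect.** By the normal approximation, 50 per arm detects (1.960 + 0.842) × √(2/50) = 0.56 SD with 80% power and (1.960 + 1.282) × 0.2 = 0.65 SD with 90% power. An expectation shift of that size would look the same as the effect sought.

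**The case against.** The strongest reply is that the protocol claims less than the word placebo suggests. It never uses the word blind. One sentence says the cover lacks the active weight, another says it looks the same, and Power Calculation concedes a control effect. On that reading the fault is an overstrong label, not a false statement that patients are masked. This is fair. But the label stands in the primary aim and decides how a positive result will be described, so it still needs correcting.

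It can also be said that the shift sizes are assumed and that the table would fit any trial with 50 per arm. That is true. The table shows how sensitive the conclusion is and measures nothing about these patients.

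A reader might infer more than the documents support:

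- *That self-rated differences cannot reflect weight at all.* They may. The design cannot say how much is weight and how much is expectation.
- *That the weekly calls unmask the rater.* The calls gather how the blanket was used, which is not necessarily which blanket it was. The caller is not named, and the primary data come from the final visit. What stands is that the arrangement is left open.
- *That entry selects patients who believe in the blanket.* The Patients section refers to expected use after the physician's assessment. That is not the patient's belief in benefit, and it applies to both arms before randomisation.
- *That patients certainly know their arm.* This is probable, but what they were told about the arms is not shown.

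**Conclusion.** The point holds in this form. The protocol describes the light cover as a placebo on grounds that do not conceal weight, and masking of patients is a property the design very probably lacks. A week-4 difference on ISI, FSI, HAD or the blanket rating scale would estimate the weighted blanket together with the expectation it raises. A real effect of weight may be part of it. Actigraph data are less exposed to reporting bias, but not wholly protected, since a patient who knows the arm may also change sleep behaviour.

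For scale, an expectation shift of 0.2 to 0.4 SD with no weight effect would give a significant result in about 17% to 51% of trials instead of 5%. This assumes equal arms of 50, a two-sided test, and shift sizes not found in the protocol. Randomisation is unaffected and the trial can run. What changes is the conclusion it may draw.

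**What to change.** 1. **Label and claim.** In Purpose and Procedure, replace *placebo* with *light-blanket control of the same appearance; patients are not masked to weight*. Add that self-rated results estimate the effect of the weighted blanket including expectation, and will be read alongside the actigraph data.
2. **Expectation.** Take one 0–10 expectation rating at the end of the baseline week, before allocation. Report the week-4 effect by it descriptively; about 100 patients are too few to rest a firm conclusion on that breakdown.
3. **Calls.** Tell patients not to disclose their blanket to the rater. In the weekly contact, ask the scales before the questions on blanket use. Have the use questions asked by someone other than the final-visit rater, for example the person who already hands out and collects the blankets. That person should take no ratings, because he or she knows every allocation and the protocol already keeps that role apart from rating.

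The cost is a few lines of text, one short question at an existing contact, one instruction to patients, and a division of the weekly call between existing staff. No blanket changes. The real downside for the sponsor is that the resulting claim is less favourable than superiority to placebo.
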